Assessment Procedures: Assessments for both conditions will occur at baseline, post-intervention (2 months) and 6 months after baseline. They will minimize participant burden while assessing key constructs of the intervention. Assessments will be administered in a quiet location at school; we expect the battery of self-report and performance measures will take 60-90 minutes. Questionnaires will be administered via tablet, using REDCap to reduce errors and missing values. We will use calendar-aided recall cues and anticipate that recall will be excellent given the salience of risk events for early adolescents. The proposed battery is shorter than that of Project TRAC, which was well-tolerated. Performance measures of emotional competence will be collected via laptop computer. The brief parent battery will be collected via REDCap and can be administered in person, via email link, or, if needed, by phone.

Measures

Primary Outcome: It is well-established that sexual self-efficacy (SSE) is correlated with positive sexual behavior outcomes and sexual well-being among a diverse array of populations¹¹²⁻¹¹⁵. As such, measuring self-efficacy for safer sexual activity as a main outcome will indicate iTRAC-SRP's efficacy and ability to promote healthier sexual behaviors with the full sample (not just those who are sexually active). Adolescents' perceived abilities to engage in behaviors that mitigate sexual risk will be assessed by the Self-Efficacy for HIV Prevention scale (12 items)¹¹⁶. This continuously scaled measure includes items such as "If you decide to have sexual intercourse with your girlfriend/boyfriend, how sure are you that you could talk to your girlfriend/boyfriend about safer sex?" The measure assesses a range of behaviors related to prevention of HIV, other STIs, or unintended pregnancy, including refusing sexual behaviors, discussing sexual histories with partners, buying condoms, taking free condoms, carrying condoms, and asking a partner to use a condom. Participants respond on a 4-point scale (couldn't do it, unsure, sure, very sure). This measure demonstrated good reliability in the TRAC study with this age group ($\alpha = .90$).

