Secondary Outcomes: Sexual Risk Cognitions: The intervention is expected to have an impact on other cognitive constructs related to sexuality (e.g., knowledge, attitudes), as well as behaviors. The Sexuality Questionnaire for Adolescents (34 items) is a multiple choice test to assess sexual health knowledge and has been shown to be sensitive to intervention impact.¹² The Abstinence Attitudes (10 items¹¹⁷) questionnaire assesses agreement with values related to abstinence ($\alpha = .86$).

Sexual Behaviors: The Adolescent Risk Behavior Assessment (ARBA)¹¹⁸ is a computer-assisted structured interview for self-reported sexual and drug behaviors, successfully used in Project TRAC. The ARBA employs a skip structure so that questions answered in the negative are not followed by more detailed questions. Questions are asked in behavioral terms, without reference to sex of partner. Except at 2-month follow-up (which will use an abbreviated version), the ARBA will assess sexual behavior occurrence and frequency in the past 6 months. Given the relative infrequency of these behaviors and their significance to adolescents, we anticipate that recall will be excellent for this time frame. For early adolescents, we have modified the ARBA to include behaviors relevant to this developmental period (e.g., genital fondling) using previously validated items from the Psychosexual Development Interview (PDI)¹¹⁹. Other questions cover condom use and number of partners. It is expected that, as in TRAC, the ER skills taught in iTRAC-SRP will result in less sexual behavior and less sexual risk when compared to the waitlist control group over the same time period. Occurrence of vaginal, anal, and oral sex, as well as condomless sex, multiple partners, and substance use before sex, assessed via ARBA, will be examined. We recognize that the study will be underpowered to detect significant group differences on these variables, given that most early adolescents will not transition to sex in this 6-month time frame of 7th grade and that larger studies with longer follow-ups will be needed to demonstrate effects on these variables. Nonetheless, gathering preliminary information will be useful for understanding the impact of iTRAC-SRP and planning for future studies.

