Data Analysis: A more detailed description of the analytic plan and justification for power calculations is presented in Section 4.4 Statistical Design and Power, including approaches to evaluate model assumptions, potential imbalance between treatment groups in baseline characteristics, and missing data. Analysis of covariance will be used to evaluate changes in self-efficacy for sexual risk prevention skills over 6-months post intervention with baseline as a covariate. All participants who were randomized will be included in all analyses (i.e., intent-to-treat). The size of the treatment effect will be estimated using standardized mean differences. The same approach will be used to evaluate sexual health knowledge and emotional competencies. Sexual behaviors (number of sexual behaviors, number of condomless sex acts) will each be aggregated across the two- and six-month follow-up assessments and analyzed using generalized linear models with log link functions and negative-binomial distributions for behavioral counts that are expected to follow a zero-altered count distribution. Exploratory analyses: Mediation: Causal mediation models will be used to test how much of the treatment effect is accounted for by measures of emotional competencies and sexual attitudes. Causal mediation provides a general framework for evaluating mediation in both linear and nonlinear models, including count outcomes¹. Moderation: To better understand who is benefiting most from the intervention we will use causal random forests, a non-parametric data-mining procedure². Although this principled exploratory approach cannot definitively define subgroups, it has better statistical properties than looking at individual moderators and will help suggest subgroups that differ in terms of their response to the intervention.

Power and Sample Size: This trial was powered to the primary and other continuously scaled outcomes (self-efficacy, knowledge, and emotional competencies). With 120 participants, this study is powered at .80 to detect moderate effect sizes (standardized mean difference $d \geq .47$). The power analysis was run using the R package simstudy v0.2.1 and assumed a two tailed type-1 error rate of .05 and a correlation between baseline and

the 6-month outcome of $r=.6$. Effect sizes from our previous work with TRAC and iTRAC showed effect sizes ranging from .20 to .70.

Deliverable: A summary report of the trial data will be created and submitted for publication.

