Participants in the Randomized Trial (Phase 2) will complete audio computer-assisted self-interviews (ACASI) on laptops at baseline, 2-, and 6-months after baseline. Adolescents will complete several questionnaires assessing demographic information, sexual attitudes and cognitions, risk behaviors, and emotional functioning. Parents will complete a locator form to assist in retention and tracking, as well as measures of demographic information and their adolescent's emotion regulation. Teens will also complete performance measures related to emotion regulation (Behavioral Indicator of Resilience to Distress; Diagnostic Analysis of Nonverbal Accuracy-2).

c. Potential Risks

The risks in this study are considered minimal. During the Translation phase, participation requires only attendance at Advisory Board meetings where opinions will be shared, though participants will be advised that they may decline to answer any questions at any time. During Acceptability Testing, participation requires completion of the web-based program across several sessions, and completion of measures and interviews that assess the acceptability and clarity of the web-based program. Similarly, during the RCT, participation requires completion of measures as described above and participation in the finalized web-based program.

Some adolescents and parents may feel uncomfortable with the topics regarding sexual health. Families are notified of this content during the informed consent process. These topics will be discussed sensitively and openly, in a developmentally appropriate way during all phases of the project. Moderators during feedback

sessions will be trained to help participants with topics of sex and sexuality. In addition, they will heavily encourage confidentiality and respect.

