3. POTENTIAL BENEFITS OF THE PROPOSED RESEARCH TO THE SUBJECTS AND OTHERS

We hope that the emotion regulation training of the iTRAC intervention will be successful in reducing the rates of sexual onset and other health risks in our subject population. Waitlist control participants will be provided the opportunity to complete iTRAC-SRP after a 6-month delay. We believe that the clear examination of these questions outweighs the previously mentioned risks. Youth have an opportunity to learn emotion regulation strategies and consider safer sexual behavior to avoid future risks. The potential benefits to individual subjects outweigh potential risks, particularly in offering adolescents a chance to better understand the nature and consequences of their risk behaviors and to learn skills related to emotion regulation.

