Secondary Outcomes: Secondary outcomes include sexual health knowledge, abstinence attitudes, sexual behaviors, and condomless sex acts. Sexual health knowledge will be analyzed like the primary outcome. Sexual behaviors will be summed across the follow-up assessments. Multiple imputation will be used to address missing assessments and the summation will occur within each imputation to ensure that missing assessment are appropriately counted. These data are expected to be zero-altered and will thus be analyzed using generalized linear models with a negative binomial distribution and a log link function. Condomless sex acts will be analyzed like sexual behaviors.

Mechanisms: Measures of mechanisms include theoretically important emotional competencies (e.g., emotion regulation, emotion recognition, distress tolerance) that mediate risk as measured by self-report, performance measures, and parent report. These outcomes will be assessed at the 2-month and 6-month follow-ups using analysis of covariance like for the primary outcome.

Power and Sample Size: This trial was powered to the continuously scaled outcomes (self-efficacy, knowledge, and emotional competencies). With 120 participants, this study is powered at .80 to detect moderate effect sizes (standardized mean difference $d \geq .47$). The power analysis was run using the R package simstudy v0.2.1 and assumed a two tailed type-1 error rate of .05 and a correlation between baseline and the 6-month outcome of $r=.6$. Effect sizes from our previous work showed effect sizes ranging from .20 to .70.

Exploratory analyses of mediation and treatment modifiers: **Mediation:** Causal mediation will be used to evaluate whether treatment-related change in self-efficacy was attributable to change in mechanisms. Causal mediation was selected because the framework can handle mediators and outcomes with non-normal distributions such as a binary outcome⁸. Mediation analyses will be run for each of the hypothesized mechanisms. **Moderation:** To better understand who is benefiting most from the intervention we will use causal random forests, a non-parametric data-mining procedure⁹. Although this principled exploratory approach cannot definitively define subgroups, it has better statistical properties than looking at individual moderators and will help suggest subgroups that differ in terms of their response to the intervention. Power was not calculated for these exploratory analyses.

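### Summing the 2-month and 6-month sexual behavior reports counts the same period twice, because the 6-month interview already covers all of follow-up

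*Combined protocol and SAP*

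**What the plan says.** Schedule. Assessment Procedures states: "Assessments for both conditions will occur at baseline, post-intervention (2 months) and 6 months after baseline". Sources of Materials, in the human subjects section, agrees: participants "will complete audio computer-assisted self-interviews (ACASI) on laptops at baseline, 2-, and 6-months after baseline". The section on potential benefits fits this too, since controls are "provided the opportunity to complete iTRAC-SRP after a 6-month delay".

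Instrument. Under Measures, the Sexual Behaviors paragraph says: "Except at 2-month follow-up (which will use an abbreviated version), the ARBA will assess sexual behavior occurrence and frequency in the past 6 months". Nothing more is said about the abbreviated form: neither its look-back, nor whether it records frequency.

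Outcome. Data Analysis says that the number of sexual behaviors and the number of condomless sex acts "will each be aggregated across the two- and six-month follow-up assessments". Statistical Design and Power, Secondary Outcomes, repeats the rule: "Sexual behaviors will be summed across the follow-up assessments", and "Condomless sex acts will be analyzed like sexual behaviors". Missing assessments are imputed first and the sum is formed within each imputed data set. The model is a negative binomial GLM with a log link; no offset is named.

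Contrary wording. Data Analysis also describes the self-efficacy analysis as running "over 6-months post intervention with baseline as a covariate".

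**The concern.** Summing reports across visits gives a total for follow-up only if the recall periods do not overlap. Here the later period contains all of follow-up, so the 2-month report adds no follow-up time. It can only repeat acts or, if its look-back is longer than 2 months, bring in acts from before baseline.

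Three things are at stake:

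- **The totals.** The protocol collects these data to inform future studies, so inflated counts would carry over into later planning.
- **The rate ratio.** Months 0-2 get extra weight. The modules take 4-8 weeks to complete, so an effect that differs between the early and later months is plausible.
- **The imputation.** A participant who misses only the 2-month visit still has a complete 6-month report. The rule would impute a 2-month count and add it, so a participant who reported no acts in 6 months could receive a positive total.

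**Working it through.** The plan gives no figure for the count outcomes, so there is none to reproduce. The check is interval arithmetic with baseline at month 0.

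**Inputs from the documents:** visits at months 2 and 6 (Assessment Procedures; Sources of Materials); 6-month look-back at the 6-month visit (Sexual Behaviors); summation of both reports (Data Analysis; Secondary Outcomes).

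**Assumed, because not documented:** the look-back L of the 2-month form, the monthly act rate f(t), and the rate ratios e in months 0-2 and r in months 2-6. Every act is taken to be reported on each form whose look-back includes it.

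**Windows.** The 6-month ARBA covers [6 - 6, 6] = months 0 to 6. The 2-month form covers [2 - L, 2].

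| L (months) | Months reported in the sum | Follow-up months counted twice | Pre-baseline months |
|---|---|---|---|
| 1 | 7 | 1 | 0 |
| 2 | 8 | 2 | 0 |
| 3 | 9 | 2 | 1 |
| 6 | 12 | 2 | 4 |

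**Over-count of acts in the control arm** = (acts in months 2 - L to 2) / (acts in months 0 to 6).

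- Constant rate: L=1, 1/6 = 17%; L=2, 2/6 = 33%; L=3, 3/6 = 50%, of which 1/6 (17 points) is pre-baseline; L=6, 6/6 = 100%, of which 4/6 (67 points) is pre-baseline.
- Rate doubling from baseline to month 6, f = 1 + t/6, with 9 units over months 0-6: L=1, 1.25/9 = 14%; L=2, 2.333/9 = 26%.
- Rate rising linearly from zero, f = t, with 18 units over months 0-6: L=1, 1.5/18 = 8%; L=2, 2/18 = 11%.

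**Rate ratio with L=2.** At a constant rate the true ratio is (2e + 4r)/6 and the summed ratio is (4e + 4r)/8. With the rate rising from zero they are (e + 8r)/9 and (2e + 8r)/10.

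| e (months 0-2) | r (months 2-6) | Rate shape | True | Summed |
|---|---|---|---|---|
| 1.00 | .50 | constant | 4/6 = .67 | 6/8 = .75 |
| 1.00 | .50 | rising from zero | 5/9 = .56 | 6/10 = .60 |
| .50 | 1.00 | constant | 5/6 = .83 | 6/8 = .75 |
| .50 | 1.00 | rising from zero | 8.5/9 = .94 | 9/10 = .90 |

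So with a look-back of 2 months or less, the ratio moves toward 1 if the effect is weaker early and away from 1 if it is stronger early.

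**Constant ratio of .50, constant rate, arms equal before baseline.** For L of 2 or less the summed ratio stays .50. For L=3 it is (8 × .50 + 1)/9 = .56. For L=6 it is (8 × .50 + 4)/12 = .67. Pre-baseline acts, on which the arms differ only by chance, pull the ratio toward 1.

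**The case against.** The strongest objection is that the defect is conditional. The abbreviated form may not record counts, in which case nothing is double-counted. But then the planned sum of acts cannot be formed, so the rule still needs repair. Double counting also requires the adolescent to report an early act again at month 6. The protocol expects excellent recall over 6 months, so on its own premise that will usually happen.

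The term for the number of sexual behaviors may mean types rather than acts. A type reported at both visits would still count twice, but the figures above would not apply.

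The wording "over 6-months post intervention with baseline as a covariate" could put the last visit near month 8. Its window would then be months 2-8 and the overlap would vanish. However, the phrase describes the self-efficacy analysis, and two explicit statements of the schedule place the visit 6 months after baseline. It needs reconciling but does not rescue the rule.

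Several points on consequence stand. Both arms follow the same schedule, so the overlap creates no group difference when there is no effect. Most participants are expected to report no sex, and two observed zeros still sum to zero. The protocol itself calls these secondary outcomes underpowered. No simple direction holds for long look-backs: with L=6, a constant rate, e=.50 and r=1.00, the true ratio is 5/6 = .83 and the summed ratio is 10/12 = .83.

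**Conclusion.** The concern holds. On the stated schedule and look-back, the 6-month ARBA covers months 0-6, and nothing in the plan removes the overlap when the 2-month report is added. The resulting total is not the number of acts in follow-up.

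The documents do not fix the size. Under the assumptions shown, the over-count runs from 8% (1-month look-back, rate rising from zero) to 100% (6-month look-back, constant rate). Whether the rate ratio moves, and in which direction, depends on the look-back and on how the effect changes over time; a constant ratio is safe only with a look-back of 2 months or less.

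This should be fixed, but it is not critical. The primary outcome and its power are untouched, and the trial belongs to Phase 2, for which approval is not yet being sought.

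**What to change.** In Data Analysis and in Statistical Design and Power, Secondary Outcomes, replace the summation rule. Define both count outcomes from the 6-month ARBA alone, as the number in the 6 months after baseline, and use the 2-month report only as an auxiliary variable in the multiple imputation. Then:

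- state the look-back and content of the abbreviated 2-month form, including whether it records frequency;
- say whether the number of sexual behaviors means acts or types;
- reconcile the post-intervention wording in Data Analysis with the visit schedule.

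An alternative is to have the 6-month form ask only about the time since the last assessment, with the 2-month form limited to the time since baseline. That keeps the shorter-recall data but changes the questionnaire and how a missed 2-month visit is handled.

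The recommended change costs one or two sentences in each analysis section and one describing the form. Visits and the 6-month questionnaire stay as they are. The small downside is that months 0-2 then rest on 6-month recall. All of this can be settled before any RCT data exist.
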